1. STUDY OBJECTIVES

To address evidence gaps regarding JITAIs, the objective of this trial is to simultaneously test innovative or adaptive intervention components, compared to their standard counterparts, that are expected to increase weight loss among YAs. This is an optimization trial, conducted as part of the Multiphase Optimization Strategy (MOST) framework.²⁴ Guided by Self-Determination Theory (SDT),²⁵ the trial will test 5 components that are designed to promote positive changes in SDT constructs: 1) diet self-monitoring approach (standard vs. simplified), 2) adaptive physical activity goals (weekly vs. daily adaptive), 3) decision points for message timing (fixed vs. adaptive), 4) decision rules for message content (standard vs. adaptive), and 5) message choice (no vs. yes).

Aim 1: Build an optimized JITAI consisting of the set of intervention components (and component levels) that yield the greatest improvement in weight change among young adults at 6 months. We will use a highly efficient experimental design, powered to detect both main effects and all two-way interactions between components. Results of the optimization experiment will be used to determine which combination of components and component levels contribute significantly to mean weight loss at 6 months. The proportion achieving 5% weight loss is our second-level decision-making criterion in cases of equal weight losses.

Aim 2: Conduct mediation analyses to test the relationships between the intervention components and hypothesized mediators. Mediators to be tested include the proximal theoretical mediators of component effects (self-regulation, competence, relatedness, relevance, autonomy) and the more distal behavioral mediators (dietary intake, physical activity, and daily self-weighing).

Aim 3: Conduct moderation analyses. The primary moderator to be tested is intervention engagement including self-monitoring engagement (weighing frequency, diet monitoring, tracker wear) and app engagement (app views, lessons, feedback, intervention message views). Exploratory moderators include gender, race/ethnicity, and initial BMI status.

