The active component levels determined from this study will be used to create an optimized just-in-time adaptive intervention that will be tested in a separate RCT to examine weight losses at 6 months with follow-up at 12 months. If the proposed aims are achieved, we will expand our understanding of ways to improve public health with just-in-time support that accounts for individual variability in lifestyle and environmental contexts. Our work advances the science of JITAI development—answering key questions about adaptation and tailoring—and is guided by a conceptual model, which will further understanding of how JITAI components and mobile interventions may operate via key theoretical mediators. Our study will be one of the first to systematically

optimize a fully automated mobile JITAI. These aims are critical initial steps for overcoming the challenge of providing and evaluating broad-reach public health interventions that are more precisely tailored to the specific characteristics of individuals.

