4. STATISTICAL CONSIDERATIONS

Sample Size and Power

We defined a 1-kg weight change as more than a minimal effect of any given component on overall weight loss. We estimated standard deviation based on a prior cell phone-delivered intervention for YAs that found a standard deviation of 6.9 kg for a weight change difference of 2.2 kg between groups;⁹ therefore, we conservatively estimated a standard deviation of 4 times our 1-kg weight change estimate. Assuming a type 1 error rate of 5% and a standard deviation of 4 kg, reaching 80% power would require 505 total participants. Assuming a 17% attrition rate at 6 months based on our previous studies with YAs and rounding up to a whole number per condition results in a total of 608 participants needed. Thus, each of the two levels of each component will have 304 randomly assigned participants, with 19 participants in each of the 32 conditions.

Statistical Analysis

Aim 1 Analysis. To test for differences in weight change across time by the five intervention components, we will use mixed effects models on an intention-to-treat data set, with effects modeled as component \times time interactions and the 6-month outcome as the primary endpoint. We will run separate models for (a) mean weight change and (b) the proportion of participants achieving 5% weight loss, the latter constituting a second-level decision-making criterion in cases where effects for mean weight change are equal. All higher-order interactions between components will also be modeled (e.g., adaptive physical activity goals \times message choice \times time interaction). The ability to test all higher-order interactions between intervention components, without reducing power, is a key advantage of the factorial experiment, as this is not possible in a traditional multi-component RCT. We will be using effect (-1,1) coding rather than dummy (0,1) coding, which keeps any covariances among main effects and interactions to a minimum. Once we have identified important effects in the initial set of models, we will establish parsimonious prediction models in which coefficients that do not contribute significantly to mean weight loss (or proportion achieving 5% weight loss) will be set to zero.

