Physical Risks: There are no major physical risks associated with the weight loss intervention or data collection. There may be some risk to increasing physical activity, including, but not limited to, injuries to the muscles, ligaments, tendons and joints of the body. Other risks include abnormal blood pressure, fainting, dizziness, disorders of heart rhythm, exacerbation of exercise-induced asthma symptoms, and very rare instances of heart attack, stroke, or even death. Although increasing physical activity can have great benefits, participants may also experience some general fatigue, sore muscles or joints from exercising. Because several studies indicate that walking is the preferred exercise type for most adult populations, the study focuses on encouraging moderate-intensity walking. To help ensure safety, the study will follow guidelines and safety recommendations for physical activity set forth by the American College of Sports Medicine. Educational materials during the course of the intervention will educate participants on exercise safety and inform them of precautions in starting an exercise program and how to manage increasing amounts of exercise. Messages will encourage participants to start at a reasonable frequency and intensity of exercise based on their current level and to increase their exercise gradually. The informed consent will also clearly communicate the potential physical risks related to starting an exercise program and increasing physical activity. Participation is fully voluntary, and we will ask participants to report any problems to the study researchers. There is a rare, but possible, risk of extreme dieting in this intervention. However, the intervention recommendations are geared toward simplified dietary changes and should be of very low risk. The greatest concerns are that participants may engage in unsafe dietary practices, lose weight more quickly or to lower levels than recommended, or develop untoward psychological

reactions. However, prior weight loss studies indicate that participants in these programs increase their use of healthy weight control practices and decrease their use of unhealthy practices.

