Protections against Psychological Risks: As noted above, participants are not required to share this information and can elect not to share sensitive and confidential information with the study. Participants will be encouraged to contact the Principal Investigator if they feel they have incurred any emotional distress as a result of study participation. As this is a voluntary study, a participant is free to exit at any point if discomfort should occur. Individuals scoring >16 on the Center for Epidemiological Studies Depression Scale (CES-D) at baseline, 3- or 6-month assessments (indicating levels of depressive symptoms that might benefit from follow up with a health care provider) will be given a letter explaining the survey and providing information and referral to resources (Appendix).

Protections against Physical Risks: To ensure medical readiness to begin physical activity, participants will complete a physical activity readiness questionnaire (PAR-Q). The PAR-Q assesses for the following medical conditions: heart problems, chest pains, faintness or dizzy spells, high blood pressure, bone or joint problems such as arthritis that has been or could be aggravated by exercise, prescription medication use, and other medical reasons why exercise would not be advisable. Participants endorsing yes to any items 1-4 on the PAR-Q (experience of heart problems, frequent chest pains, faintness or dizziness, bone or joint problems) will be excluded from the study. We also will monitor any major musculoskeletal problems that develop during the intervention (e.g. broken bones) using a medical events questionnaire at 3 and 6 months and will determine whether these appear related to our study. Participants who develop musculoskeletal problems or other health problems that may affect safe participation will be instructed to stop exercising until the problem resolves and their physician approves resumption of physical activity.

All participants will be advised about safe weight loss practices including dietary change and increasing physical activity at their initial study visit. Participants will be advised to gradually increase their physical activity and to

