use walking as a primary form of activity and will be taught that the appropriate rate of weight loss is 1 to 2 pounds per week. In addition, we will carefully monitor changes in weight during our trial. We will collect information at each assessment timepoint on hospitalizations for any psychiatric problem, including depression and eating disorders. We will track weight changes using smart scale weights and will identify any individual who loses more than 20% of their body weight, has a BMI ≤ 18.5 kg/m² at any point during the program, or loses more than 15 pounds in any month during the trial. We will have a telephone call with these participants within 2 weeks, discuss our concerns with them, and make referrals if appropriate. If there is no improvement in weight status, the participant will be unable to continue to participate in the intervention.

Protections to Ensure Confidentiality of Participants: All data records related to a participant's involvement in this research study will be stored in a locked file cabinet and/or in encrypted files on servers that adhere to the University policy on storage and transmission of sensitive data. Participant identity on these records will be indicated by an ID number, and the information linking these numbers with participant identity will be kept separate from the research records. In addition, all research databases will have password-controlled access, and this will be controlled by critical staff. Participants will be encouraged to contact the Principal Investigators if they feel they have incurred any emotional distress as a result of study participation. As this is a voluntary study, a participant is free to exit at any point if discomfort should occur.

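### The plan names and collects harms but compares none of them between component levels, so levels are selected on weight outcomes alone

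*Combined protocol and SAP*

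**What the plan says.** **Selection.** Section 1 (Study Objectives, Aim 1) says the results will be used to "determine which combination of components and component levels contribute significantly to mean weight loss at 6 months". The proportion reaching 5% loss decides between levels with equal mean losses. Section 4 (Aim 1 Analysis) fits component models for these two outcomes only; Aim 2 is mediation and Aim 3 is moderation. Section 1 then says: "The active component levels determined from this study will be used to create an optimized just-in-time adaptive intervention", which goes to a separate RCT.

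**Harms named.** Section 5 (Physical Risks) lists injury and other consequences of increased activity. Among its main concerns are unsafe dietary practices and that participants may "lose weight more quickly or to lower levels than recommended, or develop untoward psychological" reactions.

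**Harms collected.**
- Weight flags, section 5: "We will track weight changes using smart scale weights and will identify any individual who loses more than 20% of their body weight". Two further flags are a BMI of 18.5 or less and a loss of more than 15 pounds in a month.
- Medical events, sections 3 and 5: major musculoskeletal problems are monitored "using a medical events questionnaire at 3 and 6 months and will determine whether these appear related to our study".
- Psychiatric hospitalizations, section 5, at each assessment.
- CES-D and QEWP-5 (binge eating, loss of control, compensatory behaviours), section 3.

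**Stated uses.** Section 5 gives letters, calls, referral, stopping exercise or the intervention, a relatedness judgement, decisions on suspending and resuming the interventions, and IRB reporting.

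**The concern.** The trial exists to choose levels. Both selection criteria are weight outcomes, so if one level achieved part of its effect through unsafe loss, or brought more injuries, the planned analysis would not show it. A participant who trips a weight flag stays in the intention-to-treat analysis, where the loss simply raises that level's mean.

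Harm that differs by component is plausible for at least two factors. Diet self-monitoring changes what intake is tracked and limited, and the activity-goal factor changes how often goals move. This trial is also the place to look, because each component is randomized separately. The next RCT will test the assembled package and is described only in terms of weight loss. An excess of harm there could not be traced to one component.

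**Working it through.** **1. The plan's own sample size.** The inputs are in section 4: difference 1 kg ("We defined a 1-kg weight change as more than a minimal effect of any given component on overall weight loss"), SD 4 kg, type 1 error 5% (taken as two-sided), power 80%, attrition 17%.

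- n per level = 2 × (1.96 + 0.84)² × 4² / 1² ≈ 251, or 252 with unrounded quantiles rounded up; total 504. An exact t-test calculation gives 80.06% power at 505, matching the stated 505.
- 505 / 0.83 = 608.4, and 19 × 32 = 608. Each level has 608 / 2 = 304 randomized, and about 252 evaluable after attrition.

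**2. Is any harm compared by level?** Setting section 4 against the harms in section 5:

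| Harm data | Collected | Stated use | Compared by component level |
|---|---|---|---|
| Three weight flags | Yes | Call, referral, possible end of intervention | No |
| Medical events, musculoskeletal problems | Yes | Relatedness, stopping exercise | No |
| Serious events | Yes | IRB reporting | No |
| Psychiatric hospitalization | Yes | Participant safety monitoring | No |
| CES-D | Yes | Letter and referral | No |
| QEWP-5 | Yes | None stated | No |

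**3. What a by-level comparison could show.** The documents give no harm rates, so the rates below are assumptions.

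- Half-width of the 95% CI for a risk difference, with the same rate p in both levels: 1.96 × √(2p(1−p)/n). For p = 1%, n = 304: 1.96 × √(0.0198/304) = 1.6 points.
- Power, two-sided 5%: Φ[(|p₂−p₁| − 1.96√(2p̄(1−p̄)/n)) / √((p₁(1−p₁)+p₂(1−p₂))/n)]. For 2% v 4%, n = 304: (0.02 − 1.96 × 0.01384) / 0.01381 = −0.52, giving 30%.

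| Assumed rate | Half-width, 304 / 252 per level (points) | Other-level rate detectable at 80% power, 304 per level | Power for a doubling, 304 / 252 |
|---|---|---|---|
| 1% | 1.6 / 1.7 | 4.9% | 17% / 15% |
| 2% | 2.2 / 2.4 | 6.7% | 30% / 26% |
| 5% | 3.5 / 3.8 | 11.2% | 65% / 57% |
| 10% | 4.8 / 5.2 | 17.9% | 93% / 88% |

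- CES-D is continuous: detectable difference (1.96 + 0.84) × 2 / √505 = 0.25 SD at 80% power, before any gain from baseline adjustment.

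**4. Multiplicity.** The tables proposed below hold about 10 outcomes (3 weight flags, 2 medical-event rows, 2 serious-event rows, 2 QEWP-5 rows, CES-D). Over 5 components that is 50 contrasts. With no true differences, about 50 × 0.05 = 2.5 intervals would exclude zero by chance.

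**The case against.** The strongest reply is that little is at risk. The plan judges the risks minimal, every participant gets the same core programme, three of the five factors concern only message timing, content or choice, and the package faces a further RCT. The omission changes no planned estimate, test or sample size. All of this stands and limits the weight of the point. It does not remove it: minimal risk is an expectation, and tabulating data already in hand is the way to check it.

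Low power also stands. For harms at 1% to 5%, power for a doubling is 15% to 57% at 252 per level.

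Three stronger readings are tempting, and the documents do not support them.

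- *That safety data are used only person by person.* Section 5 also gives trial-level uses: deciding when the interventions should be suspended or resumed, and reporting to the IRB. None of these is a comparison between levels, but they exist.
- *That the plan treats excessive loss purely as benefit.* This is true only inside the selection models. Section 5 treats it as a safety concern for the individual, with a call, referral and possible exclusion from the intervention.
- *That unsafe loss could by itself produce the 1-kg component effect.* Assume a mean baseline weight of 95 kg (not in the documents), so that a 20% loss is 19 kg, and a mean loss of 4 kg (section 1.3 gives 1 to 6 kg). About 1 / (19 − 4) = 6.7% of a level, or 17 of 252, would have to move to the threshold. At the plan's SD of 4 kg, 19 kg lies 15 / 4 = 3.75 SD from the mean, where a normal model expects about 0.02 people in 252. Even at the 6.9 kg SD quoted in section 4 it expects about 4.

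**Conclusion.** The point holds as an omission in the analysis plan. Harms are named and measured, but no component-level estimate of any of them will exist when levels are chosen. The randomized comparison to supply one is already there, at 304 v 304 per component.

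The gain is modest. At assumed rates of 1% to 10% the intervals are about ±1.6 to ±4.8 points at 304 per level, enough to exclude large excesses but not to show moderate differences in rare harms. These figures rest on assumed rates and on the allocation in section 4. At 1%, only about 304 × 0.01 = 3 events per level are expected, so the simple interval formula is a rough guide there.

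Nothing here suggests that any level is harmful, or that the weight analysis is wrong. It is a cheap improvement that also serves the plan's own objective of knowing when the interventions raise a safety concern.

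**What to change.** Add to section 4 a descriptive safety analysis by the two levels of each component, giving counts, proportions and risk differences with 95% CIs for:

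- (a) each of the three weight flags in section 5, shown with self-weighing frequency by level. Detection depends on stepping on the smart scale, and Aim 2 treats self-weighing as a possible mediator of component effects, so flags may be found more often at one level than the other. The BMI flag will overlap the 20% flag: from the minimum entry BMI of 25, reaching 18.5 is a (25 − 18.5) / 25 = 26% loss;
- (b) any medical event, and musculoskeletal problems judged study-related;
- (c) serious adverse events, and psychiatric hospitalizations;
- (d) binge eating and compensatory behaviours on the QEWP-5.

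Report also the 6-month CES-D difference between levels, adjusted for baseline. State in Aim 1 that these tables are reported alongside the weight effects when the optimized package is chosen, and in section 4 that they are descriptive and not tests.

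Leave the management of individual participants unchanged. The cost is some wording and a few tables, with no new data, staff or participants. The downside is wide intervals for rare events and many contrasts, some of which will look notable by chance.

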2. INVESTIGATIONAL PLAN

Study Design

Rationale for Component Selection

We selected components to evaluate for an optimized JITAI based on empirical and theory-based support (Figure 1). Factors 1 and 2 test two different methods of dietary tracking and two methods of physical activity goal adaptation, respectively. Factors 3-5 directly affect the just-in-time (JIT) messages being delivered to participants, specifically the “when” and “what” of the JITAI. Guided by the JITAI framework, in which the goal is to intervene at the right time and with the right type of treatment, this study evaluates different methods for choosing decision points, decision rules, and intervention options.²⁶ *Decision points* are the times at which a decision is made about whether and how to intervene and can occur one or several times per day or week. At these times, *decision rules* (a set of tailoring variables and their values) are evaluated to determine which *intervention option* (type of treatment or message) to deliver, if any.²⁰⁻²⁶ In this study, all intervention options will be brief messages delivered via smartphone application; therefore, hereafter *intervention options* will be referred to as intervention messages.

Rationale of Factors/Intervention Components

Dietary Self-Monitoring Approach (Standard versus Simplified). Detailed calorie tracking is the standard form of dietary tracking in standard behavioral weight loss interventions,^{27,28} but adherence to calorie tracking declines over time^{29,30} and participants who stop tracking generally do not achieve clinically significant weight losses. Calorie tracking can be time intensive, and adherence may decline if the perceived cost of tracking does not outweigh its benefit.³¹ Given that self-monitoring is a central feature of *self-regulation*,³² there is a need to test other methods of dietary self-monitoring that might reduce burden and improve dietary self-regulation. We have conducted three pilot trials that have shown that a simplified Traffic Light approach,³³ in which participants track only their “red” (high-calorie) foods, is feasible among YAs and has similar adherence and weight losses at 6 months to detailed calorie tracking.^{17,18,34} However, few, if any, fully powered trials have directly compared detailed calorie tracking (“Standard”) with a simplified red food tracking approach (“Simplified”).

Adaptive Activity Goals (Weekly Adaptive versus Daily Adaptive). Adaptive intervention components, such as adaptive physical activity goals, may support more precise shaping of an individual’s behaviors, improve adherence, reduce treatment mismatch, and increase competence.³⁵ *Perceived competence*, or an individual’s feelings about their capabilities with respect to a behavior, has been shown to be an important predictor of weight loss,³⁶ and adoption and maintenance of physical activity.³⁷ The current standard for physical activity goal progression, in the context of weight loss, is to gradually increase goals with a fixed progression over time, regardless of an individual’s previous goal achievement, which may not be optimal for promoting behavior change³⁸ or supporting an individual’s competence related to physical activity. Adaptive goal setting, in which the goals are set based on participants’ personal activity levels, is emerging as an alternative to fixed progression goals,^{38,39} with evidence that interventions with step goals that adapted on a daily basis improved steps/day compared to static step goals.³⁸⁻⁴⁰ However, it is unclear whether this daily frequency of goal adaptation (“Daily Adaptive”) is necessary for a daily activity goal and whether it is more effective than adapting goals on a weekly basis (“Weekly Adaptive”).

Decision Time Points (Fixed versus Adaptive). In a JITAI framework, *decision points* are the times at which a decision is made about whether and how to intervene and can occur one or several times per day or per week. To date, many mobile interventions have relied on pre-specified, fixed messaging times (e.g., sending a text message at 5 pre-determined times per week).^{17,41,42} However, it is possible to collect and use behavioral and contextual data to determine the “right time” to deliver a message, such as JITAIIs that have sent messages when participants are at risk of a behavioral lapse.²³ This requires evaluating participant data throughout a longer time interval instead of pre-determining the message times. This additional level of tailoring may increase program and message relevance. The Elaboration Likelihood Model (ELM)⁴³ of message processing posits that individuals show greater elaboration or thinking about a given circumstance when they are more motivated, find the content interesting and personally relevant, and when they can process it.⁴⁴ Prior intervention studies have shown that increased *perceptions of relevance* of the program and program messaging increased intervention effects.^{45,46} However, it is not known if using participant behavioral data to determine decision points (“Adaptive”) will increase the relevance of the messages, and in turn improve outcomes compared to predetermined decision points (“Fixed”).

Decision Rules (Standard versus Adaptive). *Decision rules* are the sets of variables used to evaluate which intervention message a participant should receive and can include one or many tailoring variables. Delivering the “right message” should enhance feelings of *relatedness* or being respected and understood by the program, which is a critical aspect of autonomy support in self-determination theory (SDT).⁴⁷ Human-computer interaction research on mobile phone identity defines relatedness as the degree to which individuals feel connected when considering how they relate to their mobile phone and may also reflect the extent to which an app or mobile intervention provides support.⁴⁸ Within the context of a mobile program that delivers brief messages, the level of relatedness and personalization in message content is dependent upon the amount of behavioral and contextual data that is used to determine which message to deliver (i.e., the number of tailoring variables in a decision rule). It is currently not known whether increasing the complexity and adaptation of decision rules (“Adaptive”) will enhance the effects of JIT support compared to simpler decision rules (“Standard”).

Participant Message Choice (Choice versus No Choice). SDT posits that an individual will adopt and maintain more autonomous and self-determined motivation in an *autonomy* supportive context.^{25,49} Autonomy supportive behavioral strategies include providing individuals multiple options for change, a lack of forced behavior, and allowing individuals to share their perspectives.⁵⁰ Formative work among YAs with overweight or obesity emphasizes the desire for autonomy, flexibility, and choice in behavioral weight loss programs¹² and indicate that an approach that offers choice has potential for promoting clinically meaningful weight loss.⁷ While the option to have more frequent choices and control over the types of messages or intervention support received has been less studied in weight management, it has shown promise with other health behaviors.⁵¹ It is currently not known whether providing choice in the types of messages received will enhance the effects of JIT support and improve weight outcomes.

Core Intervention Overview

All participants will receive a core intervention modified from concepts of the Diabetes Prevention Program⁵² and adapted specifically for YAs.⁵³ The intervention is based on social cognitive and control theories focused on improving self-regulation via self-monitoring coupled with weekly tailored feedback. Participants will receive a Bluetooth-enabled scale (Fitbit Aria Air) and activity tracker (Fitbit) in the mail, followed by an introductory videochat session with an interventionist. In this session they will receive information relevant to their participation in the program, including an overview of how to use the AGILE app (for both iOS and Android) and other required apps (Fitbit; Traffic Light Log for participants assigned to it as described below), how to self-

monitor to achieve their daily goals (eating, activity, and self-weighing), and other information relevant to the conditions to which they have been randomized.

Activity, weight, and dietary data are synced to study servers and available in the AGILE app on pages that display participants' daily and overall progress towards their goals. The AGILE app also includes 24 behavioral lessons that are unlocked each week of the program. These include behavioral strategies with specific instruction on core cognitive and behavioral skills (i.e., goal setting, self-monitoring, problem solving, overcoming barriers, reaching out for social support, and cognitive restructuring). A Feedback page in the app displays weekly tailored feedback that summarizes participant progress based on weight change, self-monitoring frequency, and weekly goal achievement. Adaptive JIT intervention messages related to the components below are delivered 1-2 times per day.

Overview of Intervention Components and Messaging System

To equate frequency of message delivery across all conditions, all participants will receive 10 messages per week (1-2 messages per day), between 8:00AM and 9:00PM. Participants will receive a smartphone notification when a new message is displayed in the app. The messages are displayed on the Home page of the AGILE app and remain there until they expire at midnight. Participants can like or dislike messages with a thumbs up/thumbs down. Messages pertain to one of three behaviors (eating, activity, self-weighing) and are chosen based on decision rules that evaluate participant behavioral data at the time the rules are evaluated. A pre-determined schedule (which varies by some of the components as described below) assigns 1-2 behaviors that will be messaged on each program day, with unique decision rules for each behavior. Most intervention messages include one or two of the following message types: feedback on outcome, feedback with a data point, directive action, nondirective action, encouragement/motivation, and social comparison. Other intervention messages are short interactive action planning tools that guide the participant to develop a plan for one of their behavioral goals.

Description of Intervention Components (Factors)

Dietary Self-Monitoring Approach. Participants in this trial will be randomly assigned to a Standard or Simplified approach. Participants assigned to Standard tracking will receive a calorie goal ranging from 1425-2850 per day based on their sex and starting weight and will track their calories using the Fitbit app, which transmits to the study servers via the Fitbit API. The Simplified “red” food (RF) approach focuses on reducing overall caloric intake by tracking and reducing intake of RFs only; there are no specific goals for green and yellow foods. Participants assigned to Simplified tracking will receive a daily RF limit that ranges from 3-6 RFs per day and will track their RFs in a native Traffic Light Log app created for this study. They are not required to track their green and yellow foods but can do so if they choose. Participants will be able to see their current and historical dietary progress on the Eating page of the AGILE app, which will display RFs for the Simplified group and calories for the Standard group.

Adaptive Activity Goals. Participants will be randomized to receive weekly adaptive or daily adaptive daily physical activity goals. In the weekly adaptive group, participants will receive a new daily activity goal at the beginning of each program week and the daily goal remains constant throughout the week. In the daily adaptive group, participants will receive a new daily activity goal at the beginning of each day. Participants will use their Fitbit activity trackers to track their “active minutes” (AM), which are equivalent to moderate-to-vigorous physical activity minutes. At the beginning of the program, participants will receive a daily AM goal of 10- 20 AM per day based on their baseline level of activity during the run-in period. After the first program week or day (for weekly and daily adaptive, respectively), AM goal adaptations will be driven by an algorithm that sets the new goal as the 4th highest day of AM (55th percentile) in the prior 9 days.^{39,54}

Decision Points. Participants in this trial will be randomly assigned to fixed timing or adaptive timing. Fixed timing runs from a schedule that specifies the exact time (1-2 times per day) that the decision rules are run, though the times vary each day. In adaptive timing, the decision rules run hourly and participant data determines when the message should be sent (limited to 1-2 per day, mirroring the fixed schedule). In adaptive timing, messages can be delivered in closer proximity to when a behavior is completed (< 1 hour; to immediately reinforce goal achievement), or, if their usual behavior patterns suggest that receiving the message at the current time would not be ideal, the decision rules can continue to run and send a more appropriate message later in the day (e.g., not sending an activity reminder message at 9am if the participant does not usually exercise until after 7pm). This is done with additional variables in the adaptive timing decision rules that take into account participants' usual behavioral patterns.

Decision Rules. Participants will be randomly assigned to standard decision rules or adaptive decision rules. In standard, the decision rules include a limited set of variables representing behavioral progress from the current and prior day. In addition, participants are eligible to receive an interactive action planning tool if they are in a 2-day lapse, meaning they have not met their goal the current or prior day. In adaptive decision rules, the rules mirror the fixed rules, with additional behavioral and contextual tailoring variables that allow for consideration of past progress on the given behavior, other behaviors, and recent weight change, such that a message about a different behavior can be sent if that might be more appropriate for the participant. Also, participants in adaptive decision rules are not eligible to receive an interactive action planning tool unless they are in a behavioral lapse of at least 4 days (compared to 2 in standard). These additional tailoring variables and adjustments are designed to provide flexibility in the messages that can be sent to participants. Rather than requiring that the system send a message about the behavior that was assigned for that day, the comprehensive rules allow the system to, when needed, send a message on another behavior that would be more appropriate. As an example, a fixed decision rule for eating may evaluate yesterday's dietary goal achievement, the current day's dietary tracking, and current dietary intake compared to their goal. If the participant has tracked nothing, they will receive a message prompting them to track their foods. In adaptive decision rules, the rules will also evaluate recent goal progress and weight change, such that a participant who regularly tracks their food intake and is losing weight would not receive this reminder message; instead the system would choose a message about a different behavior. However, these messages would be delivered if this pattern repeated, or if the weight trajectory was no longer favorable.

Message Choice. Participants will be randomly assigned to choice or no choice, which differ in two ways. First, all messages have a like/dislike rating. In the choice group, participant like/dislike ratings change the probability that they will receive similar message types in the future based on their ratings. As described above, all messages were designed and coded based on the message type (feedback on outcome, feedback with a data point, directive action, nondirective action, encouragement/motivation, or social comparison). When a participant likes or dislikes a message, those data are used to increase or decrease, respectively, the probability that they will receive a similar message type for that given behavior in the future. In the no choice group all message types are equally likely to be chosen. Secondly, participants in the choice group are given more options and autonomy when completing the interactive action planning tools. In the no choice group, when an action planning tool is displayed on the Home page, the participant can select the 'Take Action' button, at which point they can view one available action planning activity. In the choice group, participants have two actions available, 'Take Action' or 'No Thanks.' If they select 'No Thanks,' the app does not provide them with any activity or messaging. If they select 'Take Action,' they are given two action planning activity options and can choose between them.

Study Population

Individuals will be eligible if they meet the following criteria: age 18-39; body mass index (BMI) of 25-45 kg/m²; English-speaking and writing; own a smartphone (iOS or Android) with a data and texting plan; and willing to be randomized to any levels of the factors. Exclusion criteria include being currently pregnant, pregnant within the past 6 months, or planning to become pregnant within the next 6 months; type 1 diabetes or receiving medical treatment for type 2 diabetes; a heart condition, chest pain, or other health problems that influence the ability to follow physical activity recommendations; lost 10 pounds or more in the past 6 months, history of weight loss surgery, or currently taking weight loss medications; report a past diagnosis of or receiving treatment for an eating disorder; hospitalization for depression or another psychiatric disorder in the past 12 months or history of bipolar or other psychotic disorder; another member of the household is a participant or staff member on this trial; currently participating in another weight loss, nutrition, or physical activity study or program. Individuals that reported joint problems, some prescription medications, or current treatment for hypertension or hyperlipidemia will be required to obtain written physician consent to participate (Appendix).

The trial is registered on clinicaltrials.gov (NCT04922216) and was approved by the Institutional Review Board at the University of North Carolina at Chapel Hill on July 26, 2022.

